2.9.1.1 Adverse events of special interest / grouping of AEs

The number (%) of patients with adverse events of special interest (AESI) will be summarized by Standardized MedDRA Query and PT. A listing will also be provided.

A Case Retrieval Sheet (CRS) with the exact composition of the AE groupings is to be used to map reported AEs to the AESI groupings. This file may be updated (i.e. it is a living document) based on review of accumulating trial data, and therefore the groupings are also subject to potential change. The most up-to-date version of the CRS will be used at the time of the analysis.

The number and percentage of patients with any AESI, having an AESI in each SOC and having each individual AE (PT) will be presented by SOC and PT.

The number and percentage of patients by AESI type along with incidence rate per patient and per 1000 injections will be provided. Incidence rate per patient is defined as number of patients in AESI type/total number of patients in safety analysis set and incidence rate per 1000 injection is define as (number of occurrence of AESI type/total number of injections)*1000.

The number and type of AESI will be plotted according to the time after last brolucizumab injection and time since first brolucizumab injection.

Summary statistics for change from baseline in BCVA after end date of AESI will be provided for each AESI type and change from baseline in BCVA will be plotted overall and for each type of AESI.

Patients demographics, baseline characteristics and medical history will be provided for AESI patient with safety set.

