Before inclusion in the study, patient must have a washout period of 4 weeks to 8 weeks (from 26 to 62 days inclusive) *versus* his/her last administration of a licensed anti-VEGF drug (i.e. Lucentis®, Eylea®).

The maximum study duration for 1 patient is 48 to 50 weeks, according to the patient schedule.

[figure not shown]
The study will consist of 2 periods (Figure 3-1):

- Open-label Treatment Period (from Screening/Baseline (Day 1) to Week 44 or Week 46 according to patient schedule)
- Follow-up Period (from Week 44 to Week 48 or from Week 46 to Week 50 according to patient schedule)

According to the patient treatment schedule, the last treatment can be at Week 44 or Week 46. If the last treatment visit is at Week 46, the End-of-study Visit will be at Week 50 (at least 4 weeks after the last injection) instead of at Week 48.

Patients will require attending 5 mandatory study visits: Screening/Baseline (Day 1), Weeks 4, 8, 16, and 48/50. The other visit time points will depend on the injection regimen of the patient.

Figure 3-1 **Study design**

^a End of treatment: Week 38/40/42/44/46 according to treatment schedule.

^b End of study: at least 4 weeks after the end of treatment. For patients receiving the last IVT at Week 46, the EOS Visit will be at Week 50, 4 weeks following their last treatment

The fellow eye will be treated at the discretion of the Investigator.

Open-label Treatment Period: from Day 1 to Week 44/46

The Screening Visit and the Baseline Visit (see [Table 8-1](#)) are the same visit.

One time re-assessment of patients will be allowed, **except** for the purpose of capturing new BCVA or imaging assessments that previously failed to qualify the patient (except if image quality is poor and needs to be redone). As long as testing can be repeated within 14 days of the first screening, the other screening assessments do not need to be repeated. If rescreening is to occur beyond 14 days from the original screening visit date, then all screening procedures must be repeated. Medical judgment should be exercised to ensure that treatment of nAMD is not withheld in order for a patient to participate in the study.

Patients must have confirmed nAMD at Screening/Baseline and have received his/her last licensed anti-VEGF injection from 4 weeks to 8 weeks (from 26 to 62 days inclusive).

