6.2.1.1 Permitted concomitant therapy requiring caution and/or action

During the study, standard of care or other treatments (according to the Investigator's practice) for nAMD and other diseases in the fellow eye are permitted at any time and must be recorded

in the appropriate eCRF page. Treatment of the fellow eye must be scheduled in a way so as not to disturb the schedule for visits and treatments in the study eye. The fellow eye must be monitored according to routine practice and AEs captured in the eCRF.

Administration of topical ocular corticosteroids in the study eye is allowed during the study. Corticosteroids administered intranasal, inhaled, intra-articular, or via non-extensive dermal route (< 20% of total body surface area) are also permitted during the study. Refer to [Section 6.2.2](#) for other routes of corticosteroid administration.

If cataract surgery were necessary, it should be scheduled ≥ 7 days after the most recent study treatment, if possible. Study treatment may be resumed ≥ 14 days after cataract surgery, assuming an absence of surgery-related complications.

If yttrium aluminum garnet laser (YAG) were necessary, it should be performed ≥ 7 days prior to the scheduled study visit.

Ideally, while adhering to the visit schedule specified in the protocol, study drug should be administered at least 7 days before or after SARS-CoV-2 vaccinations. This will allow to separate potential drug-drug interactions and side effects caused by vaccination. This 7-day time window would also be recommended for the first study treatment at the Baseline visit.

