6.2.2 Prohibited medication

Use of the treatments displayed in [Table 6-2](#) are not allowed after Screening/Baseline.

Table 6-2 Prohibited medication and procedures

Medication/procedure	Prohibition period	Action taken
Study eye		
Any periocular injection or intraocular administration of corticosteroids (except if needed as short-term treatment of AEs)	Anytime	Discontinue study treatment (except if for treatment of AEs)
Anti-VEGF therapy other than assigned study medication	Anytime	Discontinue study treatment
Panretinal laser, photodynamic therapy laser, or focal laser photocoagulation with involvement of the macular area	Anytime	Discontinue study treatment
Any investigational drug, biologic or device	Anytime	Discontinue study treatment
Systemic		
Anti-VEGF treatment	Anytime	Discontinue study treatment
Any investigational drug, biologic or device	Anytime	Discontinue study treatment
Medications known to be toxic to the lens, retina, or optic nerve, including ethambutol, chloroquine, hydroxychloroquine, deferoxamine, phenothiazines, and tamoxifen (except temporary use for COVID-19 treatment)	Anytime	Discontinue study treatment

In the fellow eye, treatment with investigational products (drug, biologic, or device) is prohibited. Any marketed medication used to treat the fellow eye should be recorded in the appropriate eCRF page.

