2.5 Treatments (study treatment, rescue medication, concomitant therapies, compliance)

2.5.1 Study treatment exposure

Extent of exposure to study treatment is calculated as the number of IVT injections received.

The following summaries will be presented:

1. Summary statistics of number of injection (n, q1, median, q3, min and max) will be provided.
2. Number of injections (n, q1, median, q3, min and max) before or at Week 8 and greater than Week 8.
3. Number of patients with injection category (1 injection, 2 injections up to the maximum number of injections) from Baseline to the end of the treatment period (Week 44/46) will be presented.
4. Treatment exposure by visit: The number and percentage of patients who received injections, missed a treatment and missed visits will be presented by visit.
5. The number of time the injection interval shorting and the number of time the injections interval increasing.
6. Summary statistics (n, mean, std, q1, median, q3, min and max) for overall duration will be provided.

The number and percentage of patients with changes in brolucizumab 6 mg treatment patterns over time (i.e. treatment interval adjustments, interruptions or permanent discontinuations) along with reasons, will be summarized. Discontinuations and primary reasons for treatment and/or study discontinuation will also be described.

Exposure data will be summarized on the SAF and the FAS. The exposure data will be listed on the FAS.

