5.5 Statistical models

The below SAS code will be used for statistical value.

Frequency and proportion:

```
proc freq data = <.....>;
  tables response_variable/ chisq;
run;
```

Summary Statistics:

Univariate procedure will be used for continuous response.

```
proc univariate data=<.....>;
  var response_variable;
  output out=<.....> n=_n mean=_mean std=_sd min=_min median=_med
  max=_max;
run;
```

95% CI

```
proc means data=adxe N NMISS CLM  ;
  var aval;
run;
```

Time to event analysis

```
proc lifetest data=combl alpha=0.05 conftype=loglog method=KM alphaqt=0.05
  outsurv=survest;
  time AVALW*cnsr(0);
run;
```

AESI reported by investigator

```
if AEDECOD in ("Anterior chamber cell", "Anterior chamber inflammation",
  "Vitritis", "Iritis", "Cyclitis", "Choroiditis", "Chorioretinitis", "Anterior
  chamber fibrin", "Uveitis", "Noninfective chorioretinitis", "Ophthalmia
  neonatorum", "Aqueous fibrin", "Uveitis-glaucoma-hyphaema syndrome", "Retinitis",
  "Tubulointerstitial nephritis and uveitis syndrome", "Toxic anterior segment
  syndrome", "Infective uveitis", "Vitreous haze", "Keratic precipitates", "Vitreous
  abscess", "Anterior chamber flare", "Cogan's syndrome", "Noninfective retinitis",
  "Oculomucocutaneous syndrome", "Eye infection intraocular", "Iridocyclitis", "Viral
  uveitis", "Viral keratouveitis", "Hypopyon", "Cyclitic membrane", "Eye
  inflammation", "Optic neuritis", "Ocular pemphigoid", "Oculorespiratory syndrome",
  "Idiopathic orbital inflammation", "Papillitis") then
  do;
    AEBODSYS1="Intraocular inflammation";
    AESI="Y";
  end;
else if AEDECOD in ("Choroidal infarction", "Eyeinfarction", "Macular ischaemia",
  "Ocular ischaemic syndrome", "Retinal artery embolism", "Retinal artery
  occlusion", "Retinal artery stenosis", "Retinal artery thrombosis", "Retinal
  infarction", "Retinal ischaemia", "Retinal vascular occlusion", "Retinal vascular
  thrombosis", "Retinal vein occlusion", "Retinal vein thrombosis", "Necrotising
  retinitis", "Ocular vasculitis", "Retinal vasculitis", "Retinal occlusive
  vasculitis") then
  do;
```

```

AEBODSYS1="Retinal Vasculitis and / or retinal vascular occlusion";
AESI="Y";
end;

```

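### The AESI rates, injection-timing plots and BCVA-after-AESI summary name no eye, so fellow-eye events can be set against study-eye brolucizumab injections

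*SAP*

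**What the plan says.** **Fellow-eye treatment is open.** Protocol Section 3: "The fellow eye will be treated at the discretion of the Investigator". Protocol 6.2.1.1 says that standard of care or other treatments "for nAMD and other diseases in the fellow eye are permitted at any time". Protocol 6.2.2 sets the only product restriction, "In the fellow eye, treatment with investigational products (drug, biologic, or device) is prohibited", and then adds: "Any marketed medication used to treat the fellow eye should be recorded in the appropriate eCRF page".

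**Fellow-eye events reach the database.** Protocol 6.2.1.1: "The fellow eye must be monitored according to routine practice and AEs captured in the eCRF".

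**The AESI rates carry no eye condition.** SAP 2.9.1.1 and interim SAP 2.10.1.1 both define the rate per 1000 injections as "number of occurrence of AESI type/total number of injections)*1000". The per-patient rate is patients with the AESI type over the Safety Set. Neither section defines total injections. The nearest definition is in SAP 2.5.1: "Extent of exposure to study treatment is calculated as the number of IVT injections received".

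**Related outputs.** The same sections plot AESIs by time since the first and the last brolucizumab injection, and summarise BCVA change after the AESI ends. Again no eye is named. The interim SAP's code (Statistical models) sets the AESI flag from the preferred term alone.

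**By-eye rules elsewhere.** SAP 2.9.1 presents ocular adverse events by study eye, fellow eye and any eye. Protocol 12.5.5.1 asks for separate study-eye and fellow-eye tables.

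**The concern.** Intraocular inflammation (IOI), retinal vasculitis (RV) and retinal vascular occlusion (RO) are the signal behind Amendments 2, 3 and 4. The AESI rates are this single-arm trial's own numerical statement on it. With no comparator arm, nothing offsets events arising from treatment of the other eye.

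Patients with a treated fellow eye should be expected. Protocol Section 5 has a rule for choosing the study eye when both qualify, and qualifying means at least three anti-VEGF injections in the previous six months. SAP 2.4.4 tabulates unilateral against bilateral nAMD.

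If IOI in a fellow eye treated with another agent is counted, it adds to the numerator while that eye's injections add nothing to the denominator. The timing plots would date the event from a brolucizumab injection given in the other eye. The BCVA summary would mostly pair it with study-eye acuity, because Protocol Section 8 collects fellow-eye data only at Screening/Baseline and Week 48/EOS.

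**Working it through.** The plan states no AESI rate, so there is no figure to reproduce. What can be worked out is the bias if the formula is applied without an eye condition.

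**Formula.** Take N patients with m study injections each and event risk s per study injection. A share b have a treated fellow eye receiving k injections, with risk f per injection.

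- Study-eye rate: N·m·s / (N·m) = s
- Any-eye events over study injections: (N·m·s + N·b·k·f) / (N·m) = s + (b·k/m)·f
- Ratio: R = 1 + b × (k/m) × (f/s)

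**Inputs.**

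- m = 6 or 7. Under the interval rules of Protocol 6.7.2, a completer could be injected at Weeks 0, 4, 8, 16, 28, 44 (six) or 0, 4, 8, 16, 24, 32, 40 (seven).
- b = 10% to 40% and k = 6 to 8. Both are assumptions; the documents give neither.
- f/s = 1 (assumed equal risk), or the ratio from the q4w comparison of brolucizumab with aflibercept in Protocol 4.2: IOI 9.3% vs 4.5%, RV 0.8% vs 0.0%, RO 2.0% vs 0.0%. Dosing frequency was the same in both arms, so the per-patient ratio stands in for a per-injection ratio: 4.5/9.3 = 0.48 for IOI and 0 for RV and RO.

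**Results.**

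| Risk ratio f/s | Low end (b = 0.1, k = 6, m = 7) | High end (b = 0.4, k = 8, m = 6) |
|---|---|---|
| 1 | 1 + 0.1 × 6/7 = 1.09 | 1 + 0.4 × 8/6 = 1.53 |
| 0.48 (IOI) | 1 + 0.086 × 0.48 = 1.04 | 1 + 0.533 × 0.48 = 1.26 |
| 0 (RV, RO) | 1.00 | 1.00 |

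**Cross-check from per-patient risks.** Take 295 patients with 6 study injections each (1770 in all), a study-eye IOI risk of 5.3% (the figure for females in the pivotal trials, Protocol 4.5), and a fellow-eye risk of 4.5% in an assumed 25% of patients.

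- Study-eye events: 295 × 0.053 = 15.6, or 8.8 per 1000 injections.
- Fellow-eye events: 295 × 0.25 × 0.045 = 3.3.
- Any-eye rate: (15.6 + 3.3)/1770 = 10.7 per 1000, a ratio of 1.21.

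Varying the treated share over 10–40%, the fellow-eye risk over 1–4.5% (lower end assumed) and the study-eye risk over 3.2–9.3% gives ratios from 1.01 (1 + 0.1 × 0.01/0.093) to 1.56 (1 + 0.4 × 0.045/0.032).

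**What the by-eye split would give if carried into 2.9.1.1 with the single denominator there.**

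| Events counted | Denominator | Matched? |
|---|---|---|
| Study eye | Study injections | Yes |
| Fellow eye | Study injections | No |
| Any eye | Study injections | No |

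One of the three rates is sound, and the SAP does not say that it is the main one.

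**The case against.** The strongest reply is that pooling across eyes is inferred from silence. SAP 2.9.1.1 is a subsection of 2.9.1, whose by-eye rule is written for ocular adverse events generally. Protocol 12.5.5.1 sets its by-eye rule in the same section that orders the AESI summaries. Nothing confines either rule to the general tables, and if it carries down, the study-eye rate is not inflated. The interim code only builds a flag, and eye can be applied afterwards as a reporting variable. The final SAP drops that code in favour of a Case Retrieval Sheet, and table shells and programming specifications are separate documents. Listings show eye and relationship to study treatment, and SAP 2.5.2 plans a summary of prior and post anti-VEGF therapies for AESIs. A careful reader could therefore separate the events.

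Much of this stands. A reader might infer that the SAP actually pools the eyes over study injections and so overstates the rate by 9–53%. The documents do not support that. Pooling is not stated, the denominator is not defined, and the upper figure needs equal risk per injection, which the protocol's own comparison does not show.

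The gap remains, however. The SAP's efficacy sections repeatedly restrict analysis to the study eye, while 2.9.1.1 has no such sentence. The by-eye rule includes an any-eye presentation, and for that and the fellow-eye rate the denominator does not match. Neither by-eye rule reaches the timing plots or the BCVA summary.

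**Conclusion.** The concern holds as a gap in specification with a known direction of bias. SAP 2.9.1.1 and its interim counterpart do not say which eye's events and injections form the AESI rates. Followed literally, with study injections as the denominator, they bias the brolucizumab rate upward. The per-patient rate takes in fellow-eye events in the same way. If the by-eye rule is applied and the study-eye rate is reported as the main one, that rate is unbiased.

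The size rests on assumptions about how many fellow eyes are treated, how often and with what. It is about 9–53% at equal risk per injection, about 4–26% for IOI at the 4.5/9.3 ratio, and near zero for RV and RO at the comparator's 0.0%. Only events starting in the on-treatment period would count. The point concerns a descriptive safety summary; the primary endpoint and sample size are untouched. It should be corrected because these rates address the trial's main safety question.

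**What to change.** In SAP 2.9.1.1:

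- Define the main AESI rates as study-eye events over study-eye brolucizumab injections, and patients with a study-eye AESI over the Safety Set. Define total injections explicitly.
- Apply the same eye condition to the plots by time since injection and to the BCVA-after-AESI summary.
- List fellow-eye AESIs separately, with the product given in that eye. If an any-eye count is kept, show it as a count and not over study injections.

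SAP 2.15 reports the interim analysis as already performed. Check any interim AESI rates for pooling, and correct or footnote them. Carry the eye condition into the program wherever the interim AESI flag is reused.

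The cost is a few sentences and one program condition. The by-eye tables already require eye location, and Protocol 6.2.2 already requires fellow-eye medication to be recorded. No new data are needed.

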After confirmation of eligibility, patients will be included and treated with brolucizumab 6 mg in a TtC regimen. A study visit schedule will be established at the time of inclusion for all patients. All efforts should be made to adhere to this study visit schedule within a \pm 7-day window. For a given protocol visit, assessments can be performed on 2 consecutive days, provided both days are within the visit window. Treatment (including at Screening/Baseline) is intended to be administered on the day of study visit, or if this is not possible, within 3 days

after the study visit when the per-protocol assessments would have taken place, in which case study treatment administration should occur within the next 24 hours. If study visit assessments and the corresponding treatment occur on separate days, a repeat safety check-up should be performed prior to treatment of the eye and results documented in the source documents.

The Screening/Baseline Visit is defined as Screening/Baseline/Day 1. For all patients, the last potential study treatment will be at the Week-44 visit or at the Week-46 visit if the patients had received the study treatment at an odd number of inspection visits (see below). The Initiation Phase starts on Day 1 and ends on Week 8. The TtC regimen spans from Week 8 until end of treatment (Week 44/46).

Patients will receive 3 consecutive injections every 4 weeks at Screening/Baseline, Week 4, and Week 8 (loading phase), which should be at least 21 days apart.

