6.7.2.2 Treat-to-Control Phase

After the Initiation Phase, the Treat-to-Control Phase will start from Week 8, where the injection interval will be extended by 4 weeks to Week 16 (according to disease activity).

The Treat-to-Control Phase rules are defined as follows:

- Following Week 8, treatment intervals will be either 8 weeks, 12 weeks, or 16 weeks. A patient must be discontinued from further study treatment if treatment is required more frequently, i.e., every 4 weeks.
- The assessment of disease activity will be performed at each visit by the Investigator.
- At Week 8, based on Investigator's judgment of visual and/or anatomic outcomes, treatment intervals will be extended by 4 weeks at a time, if there is no disease activity, i.e. no change in visual acuity and in other signs of the disease (e.g. IRF, SRF, hemorrhage, leakage, etc.). From Week 16, the injection interval can be maintained on Q8 (or Q12 from Week 28) if the Investigator deems that the patient will not benefit from treatment interval extension, with a minimal interval of 8 weeks.
- If disease activity recurs, treatment intervals should be shortened accordingly by 4 weeks at a time or to a minimal interval of 8 weeks.
- At the Investigator's discretion, an inspection visits at Week 14, i.e. 6 weeks after the 3rd injection, can be performed. If there is no disease activity in the study eye at Week 14, as assessed by the Investigator, the study treatment will not be administered; the next visit and injection will take place at Week 16. If disease activity is observed by the Investigator in the study eye at Week 14, the study treatment will be administered by the Investigator, and the subject will be discontinued from further study treatment.
- Inspection visits 10 weeks after the last injection can be performed at the Investigator's discretion when the injection interval is extended from 8 weeks to 12 weeks. If there is no disease activity in the study eye at the inspection visit as assessed by the Investigator, the study treatment will not be administered; the next visit and injection will take place 2 weeks later, i.e. 12 weeks after the previous study treatment. If disease activity is observed by the Investigator in the study eye at the inspection visit, the study treatment will be administered by the Investigator; the injection interval will be reduced to 8 weeks and the next injection visit will be 8 weeks after the inspection visit.

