- Similarly, inspection visits 14 weeks after the last injection can be performed at the Investigator's discretion when the injection interval is extended from 12 weeks to 16 weeks, respectively. If there is no disease activity in the study eye at the inspection visit as assessed by the Investigator, the study treatment will not be administered; the next visit and injection will take place 2 weeks later, i.e. 16 weeks after the previous study treatment. If disease activity is observed by the Investigator in the study eye at the inspection visit, the study treatment will be administered by the Investigator; the injection interval will be reduced to 12 weeks and the next injection visit will be 12 weeks after the inspection visit.
- The last potential study treatment may be administered at Week 44/46 according to the treatment schedule.
- A disease activity assessment will also be performed at the Week 48/EOS visit; however, no study treatment will be administered.

If a patient misses a disease activity assessment visits (Week 8 and the following), the patient should come to the visit as soon as possible. The investigator is recommended to consider the

patient to have met the disease activity criterion at the missed visit and the patient next treatment interval should be modified accordingly (e.g. shortened by 4 weeks).

If a patient misses Week 16, then the last visit values (Week 8 or Week 14) will be applied as the reference for disease activity assessments for the primary endpoint.

The different types of visits occurring through the study are summarized in [Table 6-3](#) with a description of when disease activity assessment and treatment will take place.

Table 6-3 Disease activity assessment and treatment occurrence according to visit type

Type	Study phase	Disease activity assessment	Treatment
Screening/Baseline (Day 1) Visit	Initiation Phase	Yes	Yes
Weeks 4 and 8 visits	Initiation Phase	Yes	Yes
Week 16 visit	Treat-to-Control Phase	Yes	Yes ^a
Treatment visits	Treat-to-Control Phase	Yes	Yes ^a
Inspection visits (optional)	Treat-to-Control Phase	Yes	Based on DA, as per Investigator's judgment
ETD visit and EOS visit (Week 48/50 ^b)	Follow up	Yes	No

^a Treatment according to Investigator's decision based on assessment of disease activity.

^b The EOS Visit will take place at least 4 weeks after the last injection, e.g. at Week 48 or at Week 50 for patients receiving his/her last injection at Week 46.

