Visit name	Screening/ Baseline ¹	W4	W8	W16	n ²	EOS ¹⁴ ETD ¹⁵	m ¹⁶
Week	Day 1	4	8	16	14 to 44/46	48/50 ³	
Informed consent	X						
Inclusion/exclusion criteria	X						
Demographics	X						
Vital signs ⁴	X	X	X	X	X	X	
Prior/concomitant medications (including surgery and procedures)	X	X	X	X	X	X	X
Study eye status at nAMD diagnosis	X						
History of treatment with the previous antiVEGF in the study eye	X						
Adverse events	X	X	X	X	X	X	X
BCVA score (ETDRS)	X	X	X	X	X	X	X
Ophthalmic examination and imaging ^{5,12}	X	X	X	X	X	X	
OCT ¹²	X	X	X	X	X	X	
Disease activity assessment	X	X	X	X	X	X	
Telephone follow-up post injection ¹³	X after 1st injection						

Note: Mandatory study visits are highlighted in grey.

1) The Screening/Baseline assessments are performed on the same visit.

2) The number of weeks between visits will vary depending on the disease activity and length of intervals between injections as determined by disease activity assessment. Study treatment at the optional inspection visits (6 weeks after the last injection when the interval is extended from 4 weeks to 8 weeks, 10 weeks after the last injection when the interval is extended from 8 weeks to 12 weeks, and 14 weeks

from the last injection when the interval is extended from 12 weeks to 16 weeks) is at the discretion of the Investigator based on disease activity assessment.

At the investigator's discretion, an inspection visit may be performed at Week 14. If there is no disease activity in the study eye at Week 14, the next visit and treatment will take place at Week 16. If disease activity is observed in the study eye, the study treatment will be administered and the patient will be discontinued from further study treatment.

3) According to the patient treatment schedule, the last treatment can be at Week 44 or to Week 46. If the last treatment visit is Week 46, the end of study visit will be at Week 50 (at least 4 weeks after the last injection) instead of Week 48.

4) Vital signs include sitting blood pressure and pulse rate.

5) Include slit lamp examination [REDACTED].

[REDACTED]

[REDACTED]

[REDACTED]

[REDACTED]

[REDACTED]

[REDACTED]

13) A telephone follow-up on safety should be performed one week after the first injection (a window for the phone call is +7 days). From the second injection onwards, similar phone calls should be made at investigator's discretion per local practice.

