9.1 Discontinuation

9.1.1 Discontinuation of study treatment

Discontinuation of study treatment for a patient occurs when study treatment is stopped earlier than the protocol planned duration and can be initiated by either the patient or the Investigator.

The Investigator must discontinue study treatment for a given patient if he/she believes that continuation would negatively affect the patient's well-being.

The Investigator and/or referring physician will recommend the appropriate follow-up medical care, if needed, for all patients who are prematurely withdrawn from the study.

Study treatment must be discontinued under the following circumstances:

- Patient requires treatment on a q4w interval after the initiation phase (Week 14/Week16), i.e., after the three-monthly injections at Baseline, Week 4, and Week 8, followed by the first interval extension

- Patient develops intraocular inflammation, including retinal vasculitis and/or retinal vascular occlusion
- Patient/guardian decision
- Pregnancy
- Use of prohibited treatment
- Any situation in which study participation might result in a safety risk to the patient

If premature discontinuation of study treatment occurs, the following should be done as appropriate:

- The Investigator should make a reasonable effort to understand and document the primary reason for the patient's premature discontinuation of study treatment using the appropriate eCRF page.
- Patients who prematurely discontinue study treatment for any reason should return 4 weeks after last study treatment to perform the assessments for early treatment discontinuation (ETD). Please refer to [Table 8-1](#), except for patients who withdraw their consent from the study and do not wish to do so (refer to [Section 9.1.2](#)).
- After these assessments are performed, patient can be switched to standard of care (SOC) anti-VEGF IVT as per investigators discretion. IVT injection is contraindicated in patients with active intraocular or periocular infections and in patients with active intraocular inflammation; therefore, the investigators must verify that these conditions are not present in the study eye prior to every injection.
- After premature study treatment discontinuation, at a minimum till week 48, in abbreviated visits, the following data should be collected at clinic visits or via telephone/email contact:
 - New/concomitant treatments
 - Adverse events/Serious Adverse Events
 - BCVA

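### The AESI counts plotted by time since last injection need patient time at risk beside them, because the dosing schedule alone makes the counts fall

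*SAP*

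**What the plan says.** SAP 2.9.1.1 describes the display in one sentence: "The number and type of AESI will be plotted according to the time after last brolucizumab injection and time since first brolucizumab injection". It names no number at risk and no patient time. The other AESI figures in that section are the share of patients affected and a rate defined as "number of occurrence of AESI type/total number of injections)*1000". Both are single overall values. SAP 2.5.1 tabulates injections received and missed by visit, which is not time since the last injection. Interim SAP 2.10.1.1 repeats the plots.

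The regimen determines how much time is observed at each lag:

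- Protocol Section 3: "Patients will receive 3 consecutive injections every 4 weeks at Screening/Baseline, Week 4, and Week 8 (loading phase".
- Protocol 6.7.2.2: "Following Week 8, treatment intervals will be either 8 weeks, 12 weeks, or 16 weeks", and "The last potential study treatment may be administered at Week 44/46 according to the treatment schedule".
- Some patients stop early. With disease activity at an optional Week 14 visit, the injection is given "and the subject will be discontinued from further study treatment". Protocol 9.1.1 also lists as a reason to stop: "Patient requires treatment on a q4w interval after the initiation phase (Week 14/Week16".

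The on-treatment window is defined in more than one way. SAP 2.1.1 and Protocol 12.5.5 end it 30 days after the last injection. Protocol 12.5.5.1 extends it to end of study if that is later. The interim SAP uses 28 days. SAP 2.9.1 ties the restriction to summary tables; Protocol 12.5.5 mentions figures as well. SAP 2.9.1.1 does not say which window the plots use.

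**The concern.** A plot of event counts against time since injection is naturally read as a picture of when the risk is highest. Counts can be read that way only if about the same patient time is observed at each lag. Here it is not. All injections contribute to the first four weeks, those from Week 8 onward contribute to weeks 4-8, and only the longer intervals contribute after that. A flat hazard would therefore look like a risk concentrated soon after injection, and events late in a 12- or 16-week interval would look rarer than they are. The overall rate per 1000 injections cannot correct the shape of either plot.

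**Working it through.** The documents give no figure on this point, so there is none to reproduce.

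**Inputs.** Injection weeks follow Protocol Section 3 and 6.7.2.2, with extension by 4 weeks at a time. The end of follow-up is the last injection + 30/7 = 4.29 weeks, capped at Week 48 (30-day rule), or Week 48 for everyone (end-of-study rule). The interval mix and the stop share are not in the documents. I assume equal thirds on Q8, Q12 and Q16 among those who continue, and 0% to 75% stopping after a Week 16 injection. The 10% dropout is left out.

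**Formula.** Patient-weeks in lag band a to b = sum over injections of max(0, min(L, b) - a), where L is the time to the next injection or to the end of follow-up. At a constant hazard, expected counts are proportional to patient-weeks.

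**Time since last injection, 30-day rule**

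| Schedule (injection weeks) | 0-4 | 4-8 | 8-12 | 12-16 |
|---|---|---|---|---|
| Q8: 0, 4, 8, 16, 24, 32, 40 | 28 | 16.3 | 0 | 0 |
| Q12: 0, 4, 8, 16, 28, 40 | 24 | 12.3 | 8 | 0 |
| Q16: 0, 4, 8, 16, 28, 44 | 24 | 12 | 8 | 4 |
| Stopped at Week 16: 0, 4, 8, 16 | 16 | 4.3 | 0 | 0 |
| Stopped at Week 14: 0, 4, 8, 14 | 16 | 2.3 | 0 | 0 |

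For Q8, for example, 7 × 4 = 28, and 4 × 4 + 0.29 = 16.3.

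- Equal thirds, no stops: (28 + 24 + 24)/3 = 25.3; (16.3 + 12.3 + 12)/3 = 13.5; (0 + 8 + 8)/3 = 5.3; 4/3 = 1.3. Ratio 1 : 0.53 : 0.21 : 0.05.
- 70% stopped at Week 16: 0.7 × 16 + 0.3 × 25.3 = 18.8; 0.7 × 4.3 + 0.3 × 13.5 = 7.1; 0.3 × 5.3 = 1.6; 0.3 × 1.3 = 0.4. Ratio 1 : 0.38 : 0.09 : 0.02.

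**Time since last injection, end-of-study rule.** With no stops the ratio is 1 : 0.63 : 0.21 : 0.05. With 70% stopped it is 1 : 0.55 : 0.23 : 0.17, with further time beyond 16 weeks from the stopped patients.

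Over all stop shares and both rules, the second band is 0.36-0.63 of the first and the third 0.07-0.24. These ranges hold for the equal-thirds mix. A single schedule can lie outside them (Q12 and Q16 alone give 0.33 in the third band), but patient time falls from the first band to the third in every case.

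**Time since first injection (patient time relative to Weeks 0-16)**

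| Scenario | 0-16 | 16-32 | 32-48 |
|---|---|---|---|
| No stops, 30-day rule | 1.00 | 1.00 | 0.85 |
| 30% stopped, 30-day rule | 1.00 | 0.78 | 0.59 |
| 70% stopped, 30-day rule | 1.00 | 0.49 | 0.25 |
| Any stop share, end-of-study rule | 1.00 | 1.00 | 1.00 |

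With no stops, the last entry is the mean of 12.29/16, 12.29/16 and 16/16.

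**Event numbers.** The inflammation rates quoted in the protocol run from 3.2% (males in HAWK and HARRIER, Section 4.5) to 9.3% (q4w dosing, Section 4.2). Used only as an assumed range, with one event per patient, that is 295 × 0.032 = 9.4 to 295 × 0.093 = 27.4 events. With no stops under the 30-day rule, the 12-16 week band holds 1.33/45.5 = 2.9% of patient time, so a constant hazard gives about 0.3 to 0.8 events there. The chance of an empty band is exp(-0.8) = 45% to exp(-0.28) = 76%.

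**The case against.** The plots are descriptive. A count plot correctly shows when the observed cases occurred, and the SAP draws no inference about risk from it. Overall AESI rates, a listing and by-visit exposure are planned as well. All of that stands, and it limits the weight of the point. It does not remove the problem: none of those outputs gives patient time by lag.

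Rates in the late bins will also be imprecise, with less than one event expected at 12-16 weeks. That is true, but a wide interval tells the reader the band is nearly uninformative, whereas an empty band in a count plot may be taken as reassurance.

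Three stronger readings are tempting, and the documents do not support them.

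- A reader might infer that patient time also falls steeply with time since first injection. Without early stops it is nearly flat, and under the end-of-study rule it is flat. The 25% to 35% expected without disease activity at Week 16 (Protocol 12.8) does not imply that 65% to 75% stop, because Protocol 6.7.2.2 allows Q8 to be maintained from Week 16. No stop share is stated.
- A reader might infer that onset timing is the main safety question left by the urgent safety measures. As described in the protocol, those concerned q4w dosing beyond loading and an immune-mediated mechanism. The safety endpoint is AE incidence up to Week 48.
- A reader might point to denser early contact, since a safety call is required only after the first injection. Patients are also told to report symptoms between visits, and a patient-time denominator would not correct uneven detection anyway.

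**Conclusion.** The point holds firmly for time since last injection. Raw counts would fall with lag at a constant hazard, to about half in the second band and a fifth in the third under equal thirds with no stops, and in the same direction under each schedule and both windows examined. The exact ratios rest on the assumed interval mix and stop share. The 12-16 week ratio is the least stable: at 70% stopped it is 0.02 under the 30-day rule and 0.17 under the end-of-study rule.

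For time since first injection the point is conditional on a substantial stop share together with the 30-day rule.

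The primary analysis and the AE incidence tables are unaffected. This is an inexpensive improvement to a descriptive safety display that would otherwise invite a predictable misreading.

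**What to change.** In final SAP 2.9.1.1, keep the counts and add:

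1. Patient-weeks at risk printed under each bin: 0-4, >4-8, >8-12 and >12-16 weeks since last injection, and 0-16, >16-32 and >32 weeks since first injection. Add an open bin above 16 weeks since last injection if follow-up continues after stopping.
2. Incidence rates per 100 patient-weeks in each bin, with exact Poisson 95% confidence intervals.
3. One stated at-risk window for these plots, reconciling SAP 2.1.1 and Protocol 12.5.5 with Protocol 12.5.5.1.
4. A statement of whether a patient remains at risk after a first AESI.

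The window affects the numerator too. Protocol 9.1.1 stops treatment when inflammation develops. An event that starts more than 30 days after an injection and leads to stopping would therefore fall outside a window ending 30 days after the last injection, while patients without an event go on to the next injection and contribute that time. Events and patient time must be counted on the same basis, or the late-lag rates will be too low.

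The cost is SAP wording and a little programming from injection and event dates already collected. The downside is wide intervals in the late bins. The change belongs in the final SAP only, since SAP 2.15 reports the interim analysis as already performed.
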